7.1.2 Temporary discontinuation

Temporary intervention discontinuation may be considered by the Treating Investigator because of suspected AEs or disruption of the clinical trial due to a regional or national emergency declared by a governmental agency (Appendix 13 [[Section 10.13](#)]). For all temporary intervention discontinuations, duration should be recorded by the Investigator in the appropriate pages of the eCRF.

7.2 PARTICIPANT DISCONTINUATION/WITHDRAWAL FROM THE STUDY

- A participant may withdraw from the study at any time at his/her own request, or may be withdrawn at any time at the discretion of the Investigator for safety, behavioral, compliance, or administrative reasons. This is expected to be uncommon.
- At the time of discontinuing from the study, if possible, an early discontinuation visit should be conducted, as shown in the SoA ([Section 1.3](#)). See SoA for data to be collected at the time of study discontinuation and follow-up and for any further evaluations that need to be completed.
- The participant will be permanently discontinued from the study intervention if discontinued from the study at that time.
- If the participant withdraws consent for disclosure of future information, the Sponsor may retain and continue to use any data collected before such a withdrawal of consent.
- If a participant withdraws from the study, he/she may request destruction of any samples taken and not tested, and the Investigator must document this in the site study records.

If participants no longer wish to take the IMP, they will be encouraged to remain in the study (ie, continue participation in site visit FUP and extended FUP).

The Investigators should discuss with them key visits to attend. The value of all their study data collected during their continued involvement will be emphasized as important to the public health value of the study.

Participants who withdraw from the study intervention should be explicitly asked about the contribution of possible AEs to their decision, and any AE information elicited must be documented.

All study withdrawals should be recorded by the Investigator in the appropriate screens of the eCRF and in the participant's medical records. In the medical record, at least the date of the withdrawal and the reason should be documented.

In addition, a participant may withdraw his/her consent to stop participating in the study. Withdrawal of consent for intervention should be distinguished from withdrawal of consent for follow-up visits and from withdrawal of consent for non-participant contact follow-up, eg, medical record checks. The site should document any case of withdrawal of consent.

Participants who have withdrawn from the study cannot be reallocated (treated) in the study. Their inclusion and intervention numbers must not be reused.

7.3 LOST TO FOLLOW UP

A participant will be considered lost to follow-up if he or she repeatedly fails to return for scheduled visits and is unable to be contacted by the study site.

The following actions must be taken if a participant fails to return to the clinic for a required study visit:

- The site must attempt to contact the participant and reschedule the missed visit as soon as possible and counsel the participant on the importance of maintaining the assigned visit schedule and ascertain whether or not the participant wishes to and/or should continue in the study.
- Before a participant is deemed lost to follow-up, the Investigator or designee must make every effort to regain contact with the participant (where possible, 3 telephone calls and, if necessary, a certified letter to the participant's last known mailing address or local equivalent methods). These contact attempts should be documented in the participant's medical record.
- Should the participant continue to be unreachable, he/she will be considered to have withdrawn from the study.

Discontinuation of specific sites or of the study as a whole are handled as part of Appendix 1 (Section 10.1).

8 STUDY ASSESSMENTS AND PROCEDURES

- Study procedures and their timing are summarized in the SoA. Protocol waivers or exemptions are not allowed.
- Adherence to the study design requirements, including those specified in the SoA, is essential and required for study conduct.
- All screening evaluations must be completed and reviewed to confirm that potential participants meet all eligibility criteria. The Investigator will maintain a screening log to record details of all participants screened and to confirm eligibility or record reasons for screening failure, as applicable.
- Procedures conducted as part of the participant's routine clinical management (eg, blood count) and obtained before signing of the ICF may be utilized for screening or baseline purposes provided the procedures met the protocol-specified criteria and were performed within the time frame defined in the SoA.
- The total volume of blood required for all assessments as per protocol is expected to be within the recommended safe limit for human in clinical trials by the local Institutional Review Boards and Ethics Committees.
- For a regional or national emergency declared by a governmental agency, contingency measures are included in Appendix 13 (see [Section 10.13](#)).
- In exceptional cases, under regional or national emergencies (eg, natural disaster, epidemic/pandemic, terrorist attack), onsite visits may be replaced with telephone/remote visits. For example, patient interview for medical history/prior medications could be performed by phone, local safety labs and some efficacy assessments could be performed off-site/at the participant's home (eg, home nursing) if agreed by patient and permissible per local regulations. In such circumstances, visit window may be expanded, if needed (eg, ± 14 days for visits).

8.1 EFFICACY ASSESSMENTS

8.1.1 Efficacy assessment - Central laboratory assessments

The primary efficacy endpoint, selective secondary, and exploratory efficacy endpoints will be assessed by the central laboratory using the SAB assay (see [Section 10.9](#)). For the purpose of cPRA and anti-HLA antibody determination, unacceptable antigens are defined as those with MFI ≥ 2000 . The cPRA will be computed based on cPRA calculator developed by the Organ Procurement and Transplantation Network, with values to be provided with 2 decimal places.

Refer to the laboratory manual for details regarding sample collection, processing, storage, and shipment.

8.1.2 Efficacy assessment - Local laboratory assessment

The cPRA levels assessed by the local laboratory will be captured for the analysis of one of the secondary efficacy endpoints. Frequency of assessment will be performed as per the local standard of practice. If possible, cPRA levels should be reported to 2 decimal points (eg, 99.99%) based on cPRA calculator developed by the Organ Procurement and Transplantation Network, in addition to locally reported cPRA, with unacceptable antigens defined as those with MFI ≥ 2000 .

8.2 SAFETY ASSESSMENTS

Planned time points for all safety assessments are provided in the SoA.

8.2.1 Physical examinations

- A complete physical examination will include, at a minimum, assessments of the major body systems. Height (only at screening) and weight will also be measured and recorded.
- Investigators should pay special attention to clinical signs related to previous serious illnesses.
- Any new finding or worsening of previous finding should be reported as a new AE.

8.2.2 Vital signs

- During the treatment period, vital signs are to be monitored just before starting infusion of the IMP, 1 hour after the start of the infusion, at the end of infusion, and during the infusion if clinically indicated.
- Temperature, pulse rate, respiratory rate, and blood pressure will be assessed.
- Blood pressure and pulse measurements will be assessed with a completely automated device. Manual techniques will be used only if an automated device is not available.
- Blood pressure and pulse measurements should be preceded by at least 5 minutes of rest for the participant in a quiet setting without distractions (eg, television, cell phones).

8.2.3 ECG

A single 12-lead ECG will be obtained at screening using an ECG machine that automatically calculates the heart rate and measures PR, QRS, QT, and QTc intervals.

8.2.4 Echocardiography

Two-dimensional echocardiography coupled with Doppler flow studies will be performed at screening to evaluate the left ventricular ejection fraction and other relevant cardiac function assessments, as needed. Echocardiography should be performed at dry weight, and/or on a non-dialysis day.

8.2.5 Clinical safety laboratory assessments

- See Appendix 2 ([Section 10.2](#)) for the list of clinical laboratory tests to be performed and to the SoA for the timing and frequency.
- The Investigator must review the laboratory report, document this review, and record any clinically relevant changes occurring during the study in the AE section of the eCRF. The laboratory reports must be filed with the source documents. Clinically significant abnormal laboratory findings are those which are not associated with the underlying disease, unless judged by the Investigator to be more severe than expected for the participant's condition.
- All laboratory tests with values considered clinically significantly abnormal during participation in the study or after the last dose of study intervention should be repeated until the values return to normal or baseline or are no longer considered clinically significant by the Investigator or Medical Monitor.
 - If such values do not return to normal/baseline within a period of time judged reasonable by the Investigator, the etiology should be identified and the Sponsor notified.
 - All protocol-required laboratory assessments, as defined in Appendix 2 ([Section 10.2](#)), must be conducted in accordance with the laboratory manual and the SoA.
 - If laboratory values from non-protocol specified laboratory assessments performed at the institution's local laboratory require a change in participant management or are considered clinically significant by the Investigator (eg, SAE or AE or dose modification), then the results must be recorded in the eCRF.

8.3 ADVERSE EVENTS AND SERIOUS ADVERSE EVENTS

Adverse event of special interest (AESI)

An AESI is an AE (serious or nonserious) of scientific and medical concern specific to the Sponsor's product or program, for which ongoing monitoring and immediate notification by the Investigator to the Sponsor is required. Such events may require further investigation in order to characterize and understand them. Adverse events of special interest may be added, modified or removed during a study by protocol amendment.

- Pregnancy of a female participant entered in a study as well as pregnancy occurring in a female partner of a male participant entered in a study with IMP/NIMP;
 - Pregnancy occurring in a female participant entered in the clinical trial or in a female partner of a male participant entered in the clinical trial. It will be qualified as an SAE only if it fulfills one of the seriousness criteria (see Appendix 3 [[Section 10.3](#)]).
 - In the event of pregnancy in a female participant, IMP should be discontinued.
 - Follow-up of the pregnancy in a female participant or in a female partner of a male participant is mandatory until the outcome has been determined (See Appendix 4 [[Section 10.4](#)])

- Symptomatic overdose (serious or nonserious) with IMP/NIMP
 - An overdose (accidental or intentional) with isatuximab is defined as increase of at least 30% of the intended administered dose at each infusion (expressed in unit per body weight) to be administered in the specified duration or if the dose is administered in less than half the recommended duration of administration.
 - An overdose (accidental or intentional) with NIMP is defined as increase of at least 30% of the intended administered dose at each administration,
 - In case of accidental or intentional overdose with IMP/NIMP, even not fulfilling a seriousness criterion, is to be reported to the Sponsor immediately (within 24 hours) using the AE form together with the SAE complementary form to be entered in the eCRF.
 - Of note, asymptomatic overdose has to be reported as a standard AE.
- Other project specific AESI
 - Grade ≥ 3 IRs. An IR occurs typically within 24 hours from the start of the infusion.

The definitions of an AE or SAE can be found in Appendix 3 ([Section 10.3](#)).

AE will be reported by the participant (or, when appropriate, by a caregiver, surrogate, or the participant's legally authorized representative).

The Investigator and any qualified designees are responsible for detecting, documenting, and recording events that meet the definition of an AE or SAE and remain responsible for following up AEs that are serious, considered related to the study intervention or study procedures, or that caused the participant to discontinue the study intervention (see [Section 7](#)).

8.3.1 Time period and frequency for collecting AE and SAE information

All AEs and SAEs will be collected from the signing of the ICF until the time points specified in the SoA ([Section 1.3](#)).

Beyond 30 days after the last dose of IMP, only ongoing related AEs, ongoing SAEs, and new related AEs/SAEs will be followed up until resolution/stabilization.

All SAEs and AESI will be recorded and reported to the Sponsor or designee immediately and under no circumstance should this exceed 24 hours, as indicated in Appendix 3 ([Section 10.3](#)). The Investigator will submit any updated SAE data to the Sponsor within 24 hours of it being available.

Investigators are not obligated to actively seek AE or SAE after conclusion of the study participation. However, if the Investigator learns of any SAE, including a death, at any time after a participant has been discharged from the study, and he/she considers the event to be reasonably related to the study intervention or study participation, the Investigator must promptly notify the Sponsor.

8.3.2 Method of detecting AEs and SAEs

The method of recording, evaluating, and assessing causality of AE and SAE and the procedures for completing and transmitting SAE reports are provided in Appendix 3 ([Section 10.3](#)).

Care will be taken not to introduce bias when detecting AEs and/or SAEs. Open-ended and non-leading verbal questioning of the participant is the preferred method to inquire about AE occurrences.

8.3.3 Follow-up of AEs and SAEs

After the initial AE/AESI/SAE report, the Investigator is required to proactively follow each participant at subsequent visits/contacts. Beyond 30 days after the last dose of IMP, only ongoing related AEs, ongoing SAEs, and new related AEs/SAEs will be followed up until resolution/stabilization, the event is otherwise explained, or the participant is lost to follow-up (as defined in [Section 7.3](#)). Further information on follow-up procedures is given in Appendix 3 ([Section 10.3](#)).

8.3.4 Regulatory reporting requirements for SAEs

- Prompt notification by the Investigator to the Sponsor of a SAE is essential so that legal obligations and ethical responsibilities towards the safety of participants and the safety of a study intervention under clinical investigation are met.
- The Sponsor has a legal responsibility to notify both the local regulatory authority and other regulatory agencies about the safety of a study intervention under clinical investigation. The Sponsor will comply with country-specific regulatory requirements relating to safety reporting to the regulatory authority, Institutional Review Boards (IRBs)/Independent Ethics Committees (IECs), and Investigators.
- Investigator safety reports must be prepared for suspected unexpected serious adverse reactions (SUSAR) according to local regulatory requirements and Sponsor policy and forwarded to Investigators as necessary.
- Adverse events that are considered expected will be specified in the reference safety information.
- An Investigator who receives an Investigator safety report describing a SAE or other specific safety information (eg, summary or listing of SAEs) from the Sponsor will review and then file it along with the Investigator's Brochure and will notify the IRB/IEC, if appropriate according to local requirements.

8.3.5 Pregnancy

- Details of all pregnancies in any female participant and any female partner of male participant who becomes pregnant 2 weeks before the first dose of isatuximab treatment, while the male participant is in the study, and within 5 months after the last dose of isatuximab treatment will be collected.

- If a pregnancy is reported, the Investigator should inform the Sponsor within 24 hours of learning of the pregnancy and should follow the procedures outlined in Appendix 4 ([Section 10.4](#)).
- Abnormal pregnancy outcomes (eg, spontaneous abortion, fetal death, stillbirth, congenital anomalies, ectopic pregnancy) are considered SAEs.

8.3.6 Cardiovascular and death events

Cardiovascular and death events should be reported as per the protocol. See [Section 8.3](#) for details.

8.3.7 Disease-related events and/or disease-related outcomes not qualifying as AEs or SAEs

Disease-related events (DREs) are typically associated with disease progression under the study according to the Investigator's opinion, and that the Investigator deem to be obviously unrelated to the IMP.

NOTE: However, if either of the following conditions applies, then the event must be recorded and reported as an AE or SAE (instead of a DRE):

- *The event is, in the Investigator's opinion, of greater intensity, frequency, or duration than expected for the individual participant.*

OR

- *The Investigator considers that there is a reasonable possibility that the event was related to study intervention.*

In addition, death occurred beyond 30 days after the last IMP administration that is not due to an AE related to IMP, or is unrelated to ongoing AE/SAE, will not be reported as an SAE even though the event may meet the definition of a SAE.

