Coagulation	X (≤14 days prior to first IMP)	As clinically indicated											See Section 10.2				
Blood typing interference test ⁱ	X (≤14 days prior to first IMP)					X ^j (IAT)				X ⁱ (IAT)			See Section 10.10				

Procedure	Screening (up to 28 days before Day 1)	Treatment Period (12 weeks)								Site Visit FUP (26 weeks) ^a	E/D ^b	Extended FUP ^c	Notes All on-treatment procedures should be performed prior to IMP administration unless indicated otherwise				
		Cycle 1 (28 Days)				Cycle 2 (28 days)		Cycle 3 (28 days)									
		D1	D8	D15	D22	D1	D15	D1	D15								
Time Window (days)		±1	±1	±1	±1	±2	±2	±2	±2	±7	±7	±7					
cPRA and SAB assay (local laboratory assessment)	X	Perform as per local standard of practice												For unacceptable antigens, use MFI ≥2000 as positivity cut-off, and report cPRA to 2 decimal point (eg, 99.90%) See Section 8.1.2			
Blood draw for cPRA and SAB assay (central laboratory assessment)		X ^j				X		X		X (every 4 weeks) ^k	X			Refer to laboratory manual for details			
Blood draw for serum immunoglobulin levels (central laboratory assessment)		X ^j						X		X (Week 17 only) ^k	X ^l			Refer to laboratory manual for details			
Blood draw for immune cell profiling (central laboratory assessment)		X ^j						X		X (Week 17 only) ^k	X ^l			Refer to laboratory manual for details			
Blood draw for functional immune cell assay (central laboratory assessment)		X ^j						X		X (to be collected on Site Visit FUP Week 1 or E/D, if C3D1 sample not collected)				Refer to laboratory manual for details			
Isatuximab		X	X	X	X	X	X	X	X								
PK/ADA		See Pharmacokinetic/ADA Flowchart												See Section 1.3.1			

Procedure	Screening (up to 28 days before Day 1)	Treatment Period (12 weeks)								Site Visit FUP (26 weeks) ^a	E/D ^b	Extended FUP ^c	Notes All on-treatment procedures should be performed prior to IMP administration unless indicated otherwise				
		Cycle 1 (28 Days)				Cycle 2 (28 days)		Cycle 3 (28 days)									
		D1	D8	D15	D22	D1	D15	D1	D15								
Time Window (days)		±1	±1	±1	±1	±2	±2	±2	±2	±7	±7	±7					
AE review	X	←=====→								X (beyond 30 days after last dose of IMP: only ongoing related AEs, new related AEs until resolution/ stabilization)	Stabilization is defined as an AE ongoing without any change for at least 3 months						
SAE review	X	←=====→								X (beyond 30 days after last dose of IMP: only ongoing SAEs, new related SAEs until resolution/ stabilization)							

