b The table of all TEAEs presented by SOC and PT will define the presentation order for all other tables (eg, treatment-emergent SAE) presented by SOC and PT, unless otherwise specified.

Analysis of all adverse events

The overview of TEAE with the details below will be generated:

- Any TEAE (any grade)
- Any grade ≥ 3 TEAE
- Grade 5 TEAE (any TEAE with a fatal outcome during the treatment-emergent period)
- Any TE SAE (any grade)
- Any serious, treatment-related, TE SAE (any grade)
- Any TEAE leading to definitive study treatment discontinuation
- Any TE AESI
- Any TE AESI grade ≥ 3
- Any treatment-related TEAE (any grade)
- Any grade ≥ 3 treatment-related TEAE

The AE summaries of [Table 6](#) will be generated with number (%) of participants experiencing at least one event. The analyses will be performed for all grades combined and for grades ≥ 3 .

Table 6 - Analyses of adverse events

Type of AE	MedDRA levels
All TEAE	Primary SOC and PT
	Primary SOC
	PT
TEAE related to IMP treatment as per Investigator's judgment	Primary SOC and PT
Treatment-emergent SAE	Primary SOC and PT
Treatment-emergent SAE related to IMP treatment as per Investigator's judgment	Primary SOC and PT
TEAE leading to definitive study treatment discontinuation	Primary SOC and PT
TEAE leading to death (death as an outcome of the AE as reported by the Investigator in the AE page)	Primary SOC and PT
	Primary SOC and PT
Pretreatment AEs & SAEs	Overview ^a
	Primary SOC and PT
Post-treatment AEs & SAEs	Overview ^a
	Primary SOC and PT
TEAE leading to dose reduction	Primary SOC and PT
TEAE leading to dose interruption	Primary SOC and PT

a Will include the following AE categories: any AEs, any SAEs, any AEs leading to death, any AEs leading to permanent intervention discontinuation

Analysis of deaths

In addition to the analyses of deaths included in [Table 6](#) the number (%) of participants in the following categories will be provided:

- Deaths during the treatment-emergent and post-treatment periods by reason for death
- An overview of Grade 5 AEs will be provided with the following categories:
 - Grade 5 AE (TEAE and post-treatment).
 - Fatal TEAE (regardless of date of death/period).
 - Grade 5 TEAE with a fatal outcome during the treatment period,
 - Any Grade TEAE with a fatal outcome during the post-treatment period.
 - Post-treatment Grade 5 AE (excluding a TEAE that worsened to Grade 5 during the post-treatment period).
- Deaths in enrolled but not treated participants

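### Protocol 8.3.7 exempts a late death from SAE reporting if either of two conditions holds, so a death from an ongoing SAE judged unrelated is exempt although the SoA, 8.3.1 and 8.3.3 keep that SAE in scope

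*Protocol*

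**What the plan says.** Protocol 8.3.7 deals with disease-related events. After a note that sends possibly drug-related events back to AE or SAE reporting, it adds a separate rule for late deaths. A death more than 30 days after the last dose that "is not due to an AE related to IMP, or is unrelated to ongoing AE/SAE, will not be reported as an SAE", and the sentence continues that this applies even where the SAE definition is met.

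Three other places set what stays in scope after day 30:

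- Section 8.3.1: "only ongoing related AEs, ongoing SAEs, and new related AEs/SAEs will be followed up until resolution/stabilization".
- Section 8.3.3 repeats that list.
- The SAE row of the Schedule of Activities: "only ongoing SAEs, new related SAEs until resolution/ stabilization".

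None of these puts a relatedness condition on ongoing SAEs. Section 8.3.1 also gives a 24-hour limit for reporting SAEs and for sending updated SAE data.

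On the analysis side, SAP 4.7.2 has a category for "Any Grade TEAE with a fatal outcome during the post-treatment period" and one for post-treatment Grade 5 events. It also tabulates deaths in the treatment-emergent and post-treatment periods by cause.

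**The concern.** The late-death sentence has two conditions, each with its own verb, joined by *or*. Read literally, meeting one of them removes the reporting duty. That takes out deaths that the three scope statements keep in.

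The result can also be odd. Section 8.3.1 asks for prompt notification of a death reasonably related to the study "if the Investigator learns of any SAE, including a death, at any time after a participant has been discharged from the study". If 8.3.7 also exempts a related death from a new event, the rule for participants still on study is laxer than the rule for those who have left.

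The stake is the speed and attribution of late fatal events. Protocol 2.3.2.1 names opportunistic infection and second primary malignancy as risks, and both can appear after treatment ends. Section 9.5.1 provides no data monitoring committee, so SAE reports to the sponsor are a main safety channel.

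**Working it through.** The plan gives no figure to reproduce. The check is a truth table of the 8.3.7 sentence, set against the post-day-30 scope.

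**Inputs**

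- Condition A (8.3.7): the death is not due to an IMP-related AE.
- Condition B (8.3.7): the death is unrelated to an ongoing AE/SAE.
- Rule as written: exempt if A *or* B.
- Scope (8.3.1, 8.3.3, Schedule of Activities): ongoing related AEs, ongoing SAEs, and new related AEs/SAEs.
- Reading of *ongoing*: first taken as ongoing at day 30, because the scope statements contrast ongoing events with new ones.

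| Cause of death | A | B | Exempt: A *or* B | Exempt: A *and* B | In scope after day 30 |
|---|---|---|---|---|---|
| Related, ongoing at day 30 | false | false | no | no | yes |
| Related, new after day 30 | false | true | **yes** | no | **yes** |
| Unrelated, ongoing, serious at day 30 | true | false | **yes** | no | **yes** |
| Unrelated, ongoing, not serious at day 30 | true | false | yes | no | not listed |
| Unrelated, new after day 30 | true | true | yes | yes | no |

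Ignoring the serious/not serious split, there are 2 × 2 = 4 categories. *Or* exempts three and *and* exempts one. Two rows (bold) are both exempt and in scope: those are the contradictions.

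**Second reading.** Suppose *ongoing* means ongoing at the time of death. A fatal new related event is then itself ongoing, so B is false, A is false, and the death is reportable. The unrelated ongoing SAE does not change: A is true, so it is exempt whatever B is. That contradiction holds on both readings; the new related one holds only on the first.

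This reading also affects the repair. With *and*, a death from a new unrelated AE would have B false and become reportable, although such events are outside the 8.3.1 scope. The last column but one of the table therefore needs *ongoing* tied to day 30.

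**How much follow-up the rule governs.** The last planned dose is Cycle 3 Day 15, which is study day 2 × 28 + 15 = 71. The 30-day window closes at day 71 + 30 = 101. Protocol 4.1 gives about 78 weeks per participant including up to 4 weeks of screening, so 74 × 7 = 518 days from first dose. The rule covers 518 − 101 = 417 days, and 417/518 is about 80% of that time. This is a length of time, not a count of affected deaths, which the documents do not allow one to estimate.

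**The case against.** The strongest reply is that the sentence was meant as *neither related nor linked to an ongoing event*, and that its setting says so. The section is about events that the investigator considers obviously unrelated. Its note requires possibly related events to be reported as AEs or SAEs. Sections 8.3.1 and 8.3.3 and the Schedule of Activities keep new related SAEs in. For an SAE already on file, 8.3.1 also asks for updates within 24 hours, so a fatal outcome could reach the sponsor that way.

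Much of this stands as evidence of intent. It does not remove the conflict. The note concerns the classification of disease-related events, and the late-death sentence follows as an additional rule. No text says whether 8.3.7 or 8.3.1 prevails, so a site that follows 8.3.7 and a site that follows 8.3.1 would act differently on the same death.

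Two stronger inferences are tempting, and the documents do not support them.

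- *A fatal new drug-related event is plainly exempt.* That requires *ongoing* to mean ongoing at day 30. The contrast with *new* elsewhere favours this, but 8.3.7 does not say it, and the note in the same section points the other way.
- *Late deaths are lost and fatal toxicity is under-counted.* Section 8.3.7 limits reporting as an SAE only. Survival status is collected in follow-up (Schedule of Activities, footnote o). The SAP table of deaths by cause carries no SAE condition, and its table of AEs leading to death draws on the outcome entered on the AE page.

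**Conclusion.** The late-death rule in 8.3.7 is wrong as written. For a death from an SAE ongoing at day 30 and judged unrelated, it contradicts 8.3.1, 8.3.3 and the Schedule of Activities on either reading of *ongoing*. For a fatal new IMP-related event, the contradiction depends on the day-30 reading. For an unrelated AE that was ongoing but not serious at day 30, there is a gap and not a contradiction, because the other sections do not list it.

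The consequence is limited to 24-hour SAE reporting and to attribution of the death to an AE, which could affect the SAP's fatal-AE categories but not its count of deaths. For scale only, one event is 1/36 to 1/24, or 2.8% to 4.2%, of the 24 to 36 participants planned at the starting dose, and 1/42 to 1/30, or 2.4% to 3.3%, if the lower dose level is used. Neither range estimates how many deaths would be affected.

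**What to change.** In Protocol 8.3.7, replace *or* with *and*, so that a death more than 30 days after the last dose is exempt only if it is neither due to an IMP-related AE nor linked to an ongoing AE/SAE. In the same edit:

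- State that *ongoing* refers to the 30-day point, in line with its use in the Schedule of Activities, 8.3.1 and 8.3.3.
- State whether a death from an ongoing unrelated AE that was not serious at day 30 is reportable. *And* makes it so, while 8.3.1 does not list it.
- Reconcile the sentence with those three places so that one rule applies.

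The cost is a short protocol correction and a clarification to sites, with possibly a few more SAE reports. No analysis in the SAP needs to change.
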